4.7 End of study definition

The end of the study is defined as the date of the last visit of the last participant in the study.

Study completion is defined as when the last participant finishes their last study visit and any repeat assessments associated with this visit have been documented and followed-up appropriately by the investigator.

5 Study population

The study population will be comprised of hospitalized male and female patients with a diagnosis of sepsis and AKI. Approximately 20 participants will be enrolled in the study and randomized to receive either TIN816 or placebo.

The investigator must ensure that all participants being considered for the study meet the following eligibility criteria. No additional criteria should be applied by the investigator in order to ensure that the study population will be representative of all eligible participants. Deviation from any entry criterion excludes a participant from enrollment into the study. Replacement participants may be enrolled to replace participants who discontinue the study for reasons other than safety, based on the sponsor's decision.

In the case where a safety laboratory assessment at screening is outside of the range specified below, the assessment may be repeated once prior to randomization. If the repeat value remains outside of the specified ranges, the participant is excluded from the study.

5.1 Inclusion criteria

Participants eligible for inclusion in this study must meet **all** of the following criteria at screening assessment, unless otherwise specified at randomization (Day 1) :

1. Signed informed consent must be obtained prior to participation in the study.
2. ≥ 18 and ≤ 85 years of age.
3. Admitted to ICU or intermediate/HDU.
4. Diagnosis of sepsis according to criteria defined by The Third International Consensus Definitions for Sepsis and Septic Shock (Sepsis-3) based on:

- Suspected or confirmed infection
- SOFA score of 2 or more (excluding renal component)

5. Diagnosis of AKI Stage 1 or greater per the following criterion at randomization :

- An absolute increase in serum or plasma creatinine (CR) by ≥ 0.3 mg/dL (≥ 26.5 μ mol/L) within 48 hours or presumed to have occurred in the previous 48 hours as compared to the reference creatinine baseline
- For hospital-acquired AKI, a stable serum creatinine obtained in the hospital prior to AKI should be used as reference baseline, otherwise, baseline serum creatinine in the following order of preference:
 1. Median value within 3 months of the hospital admission. If not available:
 2. Median value between 3 and 6 months prior to hospital admission. If not available:
 3. At hospital admission.

5.2 Exclusion criteria

Participants meeting any of the following criteria at screening assessment, unless otherwise specified at randomization (Day 1) , are not eligible for inclusion in this study.

1. Not expected to survive for 24 hours.
2. Not expected to survive for 30 days due to medical conditions other than SA-AKI.
3. History of CKD with a documented estimated GFR <45 ml/min prior to development of AKI.
4. Receiving RRT or a decision has been made to initiate RRT within 24 hours of admission.
5. Weight is less than 40 kg or more than 125 kg .
6. Has life support limitations (eg, do not resuscitate, do not dialyze, do not intubate).
7. AKI diagnosis according to the AKI inclusion criteria for a period longer than 48 hours prior to study drug administration.
8. Presence of AKI for a period longer than 48 hours prior to study drug administration as suggested by clinical manifestations, e.g., prolonged oliguria or severe renal dysfunction (eg, serum creatinine > 4 mg/dL) on admission without a history of CKD.
9. Evidence of recovery from AKI based on the investigator's clinical judgement prior to randomization.
10. AKI is most likely attributable to causes other than sepsis such as nephrotoxic drugs (Non-steroidal anti-inflammatory drugs (NSAIDs), contrast, aminoglycosides), other medical conditions (e.g. heart failure, liver failure, acute abdominal aortic aneurysm, dissection, renal artery stenosis) or urinary obstruction.
11. Documented (biopsy proven) or suspected history of acute or sub-acute kidney diseases such as rapidly progressive glomerular nephritis (RPGN) and acute interstitial nephritis (AIN).
12. Patients who are post-nephrectomy.
13. Patients who are on dual antiplatelet therapy.

14. Patients who are thrombocytopenic at screening (Platelet count <100,000 microliter) or other high risk for bleeding in the opinion of the investigator.
15. Immunosuppressed patients:
 - History of immunodeficiency diseases or known HIV test positive.
 - Is receiving immunosuppressant treatment or is on chronic high doses (high-dose therapy exceeding 2 weeks of treatment) of steroids equivalent to prednisone/prednisolone 0.5 mg/kg/day, including solid organ transplant patients. Patients with septic shock treated with hydrocortisone (e.g., 3 × 100 mg) can be included.
16. Active hepatitis (defined as (a) abnormal liver enzymes (Alanine aminotransferase (ALT), Gamma-glutamyl transferase (GGT), ALP > 3x Upper Limit of Normal (ULN) or (b)) for active hepatitis B or C infection, a positive Hepatitis B Virus (HBV) or Hepatitis C Virus (HCV) serology or patients with advanced chronic liver disease, confirmed by a Child-Pugh score of 10–15 (Class C).
17. Acute pancreatitis with no established source of infection.
18. Active hematological malignancy (previous hematological malignancies that are not actively treated are allowable).
19. Burns requiring ICU treatment.
20. Sepsis attributed to confirmed COVID-19.
21. Use of other investigational drugs within 5 half-lives of enrollment within 30 days (e.g., small molecules) / or until the expected pharmacodynamic effect has returned to baseline (e.g., biologics), whichever is longer; or longer if required by local regulations.
22. History of hypersensitivity to the study treatment or its excipients or to drugs of similar chemical classes.
23. Any medical conditions that could significantly increase risk of participants' safety by participating in this study according to investigator's judgement.
24. Women with a positive pregnancy test, pregnancy or breast feeding.
25. Women of child-bearing potential, defined as all women physiologically capable of becoming pregnant, unless they are using highly effective methods of contraception while taking study treatment and for 38 days of study treatment after stopping medication. Highly effective contraception methods include:
 - Total abstinence (when this is in line with the preferred and usual lifestyle of the participant. Periodic abstinence (e.g. calendar, ovulation, symptothermal, post-ovulation methods) and withdrawal are not acceptable methods of contraception
 - Female sterilization (have had surgical bilateral oophorectomy with or without hysterectomy), total hysterectomy, or bilateral tubal ligation at least six weeks before taking investigational drug. In case of oophorectomy alone, only when the reproductive status of the woman has been confirmed by follow-up hormone level assessment
 - Male sterilization (at least 6 months prior to screening). For female participants on the study, the vasectomized male partner should be the sole partner for that participant

- Use of oral (estrogen and progesterone), injected, or implanted hormonal methods of contraception or placement of an intrauterine device (IUD) or intrauterine system (IUS), or other forms of hormonal contraception that have comparable efficacy (failure rate < 1%), for example hormone vaginal ring or transdermal hormone contraception.

In case of use of oral contraception women should have been stable on the same pill for a minimum of 3 months before taking study treatment.

Women are considered post-menopausal if they have had 12 months of natural (spontaneous) amenorrhea with an appropriate clinical profile (e.g. age-appropriate history of vasomotor symptoms). Women are considered not of child-bearing potential if they are post-menopausal or have had surgical bilateral oophorectomy (with or without hysterectomy), total hysterectomy or bilateral tubal ligation at least six weeks prior to enrollment on study. In the case of oophorectomy alone, only when the reproductive status of the woman has been confirmed by follow-up hormone level assessment is she considered to be not of child-bearing potential.

If local regulations are more stringent from the contraception methods listed above to prevent pregnancy, local regulations apply and will be described in the ICF.

5.3 Screen failures

A screen failure occurs when a participant who consents to participate in the clinical study is subsequently found to be ineligible and therefore not randomly assigned to study treatment. A minimal set of screen failure information is required to ensure transparent reporting of screen failure participants to meet the Consolidated Standards of Reporting Trials (CONSORT) publishing requirements and to respond to queries from regulatory authorities. Minimal information includes demography, screen failure details, eligibility criteria, and any SAE.

No rescreening is permitted in this study.

5.3.1 Participant numbering

Each participant is identified in the study by a participant number (Participant No.), that is assigned when the participant is enrolled for screening and is retained for the participant throughout his/her participation in the study. The Participant No. consists of the Site Number (Site No.) (as assigned by Novartis to the investigative site) with a sequential participant number suffixed to it, so that each participant's participation is numbered uniquely across the entire database. Upon signing the informed consent form, the participant is assigned to the next sequential Participant No. available.

6 Study treatment(s) and concomitant therapy

The investigational drug, TIN816 will be manufactured by Novartis and supplied to the unblinded site pharmacist or unblinded qualified site designee. The unblinded pharmacist/unblinded qualified site designee will prepare the appropriate dosage (detailed instructions will be provided in the Pharmacy Manual). A blinded nurse/blinded qualified specialist will administer TIN816 (as described in the Pharmacy Manual). The placebo will be sourced locally by the study site as 0.9% saline solution. Saline sourced locally will also be

used a dilutant during the preparation of TIN816. Preparation and administration of the study treatment will be in a blinded fashion.

Details on the requirements for storage and management of study treatment, and instructions to be followed for participant numbering and administration of the study treatment are outlined in the Pharmacy Manual.

6.1 Study treatment(s)

The investigational drug, TIN816 (Table 6-1) will be supplied as open labeled medication in vials to an unblinded site pharmacist or an unblinded qualified site designee. Each vial contains 70mg TIN816.

TIN816 is provided as a lyophilisate which needs to be reconstituted with sterile water for injection (SWFI) and, diluted using sterile 0.9% saline solution before use.

An unblinded pharmacist or an unblinded qualified site designee will prepare the investigational and control drug to dispense to the blinded staff for study drug administration. Please refer to Pharmacy Manual for detailed instructions.

Study treatment will be administered as a 2 hour IV infusion (approximately) via a perfusor syringe at the clinical site by the study personnel in accordance with the specified study procedures and the Pharmacy Manual.

All kits of study treatment assigned by the IRT will be recorded in the IRT system.

Table 6-1 Investigational and control drug

Investigational/ Control Drug (Name and Strength)	Treatment Form or Pharmaceutical Dosage Form	Route of Administration	Presentation	Sponsor (global or local)
TIN816 70mg (lyophilisate in vial)	Powder for Solution for infusion	Intravenous use	Open label supply; vials	Sponsor (global)
Placebo (Saline)	0.9% sodium chloride solution	Intravenous use	Open label infusion bags	Site (local)

6.1.1 Additional study treatments

No other study treatment beyond investigational drug are included in this study.

6.1.2 Treatment arms/group

Approximately 20 participants will be assigned at Day 1 to one of the following two treatment arms/groups in a ratio of 3:1; TIN816:placebo

- TIN816: 2 mg/kg; intravenous infusion; one-time administration
- Placebo: intravenous infusion; one-time administration

6.1.3 Treatment duration

TIN816 is a one-time, single dose treatment for SA-AKI at the randomization (Day 1) visit (refer to [Section 6.1](#)).

Study treatment drug will be administered as an 2 hour IV infusion (approximately) via a perfusor syringe at the clinical site by the study personnel in accordance with the specified study procedures.

6.2 Preparation, handling, storage, and accountability

Each study site will be supplied with study drug in packaging as described under investigational and control drugs section in [Table 6-1](#). For details on drug preparation, please refer to the Pharmacy Manual.

A unique medication number is printed on the study medication label.

An unblinded pharmacist/qualified site designee will identify the study medication kits to prepare the TIN816 treatment for this one-time administration by contacting the interactive response technology (IRT) and obtaining the medication number(s). The study medication has a 2-part label (base plus tear-off label), the unblinded site personnel (pharmacist or qualified site designee) will detach the outer part of the label from the packaging and affix it to the source document.

6.2.1 Handling of study treatment

Study treatment must be received by the unblinded pharmacist or a qualified site designee at the study site, handled and stored safely and properly and kept in a secured location to which only the unblinded pharmacist or qualified site designated site personnel have access. Upon receipt, all study treatment must be stored according to the instructions specified on the labels for TIN816 and as per packaging instructions for locally sourced saline (placebo). Clinical supplies are to be prepared and administered for IV administration only in accordance with the protocol and the Pharmacy Manual. Technical complaints are to be reported to the respective Novartis Country Organization Quality Assurance.

Medication labels will be in the local language and comply with the legal requirements of each country. They will include storage conditions for the study treatment but no information about the participant except for the medication number.

The unblinded pharmacist or unblinded designated site staff must maintain an accurate record of the shipment and dispensing of study treatment in a drug accountability log. Monitoring of drug accountability will be performed by field monitors during site or remote monitoring visits, and at the completion of the study. The unblinded pharmacist or unblinded designated site staff must provide accountability also for locally sourced materials used for administration (i.e., saline solution).

The site may destroy and document destruction of unused study treatment, drug labels and packaging, as appropriate in compliance with site processes, monitoring processes, and per local regulation/guidelines. Otherwise, the investigator will return all unused study treatment, packaging, drug labels, and a copy of the completed drug accountability log to the Novartis monitor or to the Novartis address provided in the investigator folder at each site.

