6.3 Measures to minimize bias: randomization and blinding

6.3.1 Treatment assignment, randomization

At randomization visit (Day 1), all eligible participants will be randomized via IRT to one of the treatment arms. The investigator or his/her delegate will contact the IRT after confirming that the participant fulfills all the inclusion/exclusion criteria. The IRT will assign a randomization number to the participant, which will be used to link the participant to a treatment arm and will specify unique medication numbers of study treatment TIN816 to be administered to the participant or placebo treatment administered as 0.9% saline solution, sourced locally.

The randomization numbers will be generated using the following procedure to ensure that treatment assignment is unbiased and concealed from participants and investigator staff. A participant randomization list will be produced by the IRT provider using a validated system that automates the random assignment of participant numbers to randomization numbers. These randomization numbers are linked to the different treatment arms, which in turn are linked to medication numbers. A separate medication list will be produced by or under the responsibility of Novartis Global clinical supply (GCS) using a validated system that automates the random assignment of medication numbers to packs containing the study treatment.

The randomization scheme for participants will be reviewed and approved by a member of the Randomization Office.

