6.3.2 Treatment blinding

Participants, investigator staff, and persons performing the assessments will remain blind to the identity of the treatment from the time of randomization until database lock. All unblinded personnel will keep randomization lists and data or information that could unblind other study team members confidential and secure except as described below.

Novartis Clinical Trial Team (CTT), including sample analyst(s) (PK, PD [REDACTED]) will be unblinded to the identity of treatment and will have full access to trial data.

Site staff

With the exception of any unblinded site staff identified below, all site staff (including study investigator and study nurse) will be blinded to study treatment throughout the study.

Unblinding a single participant at site for safety reasons (necessary for participant management) will occur via an emergency system in place at the site.

Sponsor staff

In addition to Novartis CTT, the following unblinded sponsor roles are required for this study.

- Unblinded field monitor(s)
- Unblinded clinical staff managing drug re-supply to site

The unblinded field monitors are required to review drug accountability and allocation at site. The unblinded monitors are not provided with a randomization list directly but will be unblinded through review of source documentation compiled by the unblinded pharmacist, which details treatment allocation to individual participants. The unblinded monitors will also be able to review the treatment allocation provided by IRT to the unblinded pharmacist.

If sponsor clinical staff are required to assist in the management and re-supply of investigational drug product, these individuals are not provided with randomization lists directly, but may be unblinded through communication of drug re-supply needs via the unblinded site pharmacists.

The sample analysts will receive a copy of the randomization schedule (via request to the Randomization Office), to facilitate analysis of the samples. The sample analysts will provide the sample data to the study team.

The study statistician will be able to access the full randomization list from the start of the study and is allowed to share unblinded information with the rest of the clinical trial team as appropriate for internal decision purposes. For example, unblinded summaries and unblinded individual data can be shared with the team whenever necessary.

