6.4 Study treatment compliance

An one time intravenous infusion will be administered in the ICU/HDU. This information must be captured in the source document, the appropriate eCRF and in the Drug Accountability Log. The site personnel should reflect total volume administered as well as the date and time of administration in the eCRF page. Any reason for dose interruption of the IV infusion will also be captured in the source document and the eCRF.

PK parameters (measures of treatment exposure) will be determined in all participants treated with TIN816, as detailed in PK section ([Section 8.7](#)).

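### Section 6.2.1 gives the blinded investigator the return of drug labels and the completed accountability log, which contradicts the site blind in 6.3.2

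*Protocol*

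**What the plan says.** Protocol 6.3.2 sets the blind: "Participants, investigator staff, and persons performing the assessments will remain blind to the identity of the treatment from the time of randomization until database lock". It adds that, apart from the named unblinded staff, "all site staff (including study investigator and study nurse) will be blinded to study treatment throughout the study". It obliges unblinded personnel to keep anything that could unblind others secure, and it names unblinded field monitors as the people who review accountability and allocation at the site.

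Protocol 6.2.1 governs handling. Study drug is "kept in a secured location to which only the unblinded pharmacist or qualified site designated site personnel have access". The accountability log is kept by the unblinded pharmacist or other unblinded site staff, and locally sourced saline must be accounted for too. For disposal there are two routes. Under the first, "The site may destroy and document destruction of unused study treatment, drug labels and packaging". Failing that, "the investigator will return all unused study treatment, packaging, drug labels, and a copy of the completed drug accountability log to the Novartis monitor"; the sponsor address in the investigator folder is the alternative destination. The same section has accountability monitored by field monitors, without the word unblinded.

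Two neighbouring sections bear on this. In 6.2 the unblinded personnel detach the outer label of the TIN816 kit; they "will detach the outer part of the label from the packaging and affix it to the source document". In 6.3.1 the investigator or a delegate contacts the IRT after confirming eligibility, and the system "will specify unique medication numbers of study treatment TIN816 to be administered to the participant or placebo treatment administered as 0.9% saline solution, sourced locally".

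**The concern.** The arms are physically different. Sections 6 and 6.1 describe TIN816 as open-label vials prepared by an unblinded pharmacist, and placebo as ordinary local saline with no sponsor kit. A kit label or medication number linked to a participant, or a dispensing entry, therefore identifies the arm. Section 6.2.1 puts those records in the hands of the investigator, whom 6.3.2 lists by name as blinded.

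The investigator judges whether each adverse event is related to study treatment (8.6.1). That judgement feeds a separate summary of treatment-related events (Protocol 9.4.2, SAP 2.6.1) and bears on how bleeding, an event of special interest (8.6.6), is reported. Section 4.2 gives control of bias in assessing safety and efficacy as the reason for the blind, and safety against placebo is the secondary objective. With about 20 participants allocated 3:1, roughly 15 receive TIN816 and 5 placebo, so a few altered causality judgements could change the look of the comparison.

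**Working it through.** The plan states no figure on this point, so the check is mainly a comparison of sections.

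**Does the material reveal the arm?** Inputs: 2 mg/kg (6.1.2), 70 mg per vial (6.1), weight limits 40 to 125 kg (5.2). Vials per TIN816 participant = dose / 70 mg, rounded up, assuming no overfill.
- At 40 kg: 2 × 40 = 80 mg; 80 / 70 = 1.14, so 2 vials.
- At 125 kg: 2 × 125 = 250 mg; 250 / 70 = 3.57, so 4 vials.

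A TIN816 participant uses 2 to 4 numbered vials and a placebo participant none. Under 3:1 allocation, always guessing TIN816 is right for 15 / 20 = 75% of participants. A participant-level dispensing entry removes the guess for that participant.

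**Is the log at participant level?** Section 6.2.1 makes it a record of shipment and dispensing. Section 6.4 requires the infusion to be entered there: "This information must be captured in the source document, the appropriate eCRF and in the Drug Accountability Log". Participant-level entries are the natural reading, though the log form itself is not in the documents.

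**Step by step:**

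| Step | Who, as written | Consistent with 6.3.2? |
|---|---|---|
| Storage of drug (6.2.1) | Unblinded pharmacist or designated personnel | Yes |
| Keeping the log (6.2.1) | Unblinded staff | Yes |
| Return of drug, labels and log copy (6.2.1) | The investigator | No |
| Accountability monitoring (6.2.1) | Field monitors, blind status not given | Incomplete: 6.3.2 says unblinded |
| Tear-off label (6.2) | Affixed by unblinded personnel; file not specified | Can be read consistently |
| Medication numbers (6.3.1) | Recipient not named | Can be read consistently |

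Only the return step names a blinded role. It also sits badly with the rest of 6.2.1, which gives storage and the log to other people.

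**When would it happen?** A completed log points to site close-out. Section 6.3.2 promises the blind until database lock, and under 10.1.5.2 site staff answer data queries and change data before lock. A return between a site's last visit and lock would leave a period in which causality entries could still be revised by someone who has handled the log.

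**The case against.** A reader might go further and infer that 6.2, 6.2.1, 6.3.1 and 6.4 together hand allocation to blinded staff, so that the blind cannot hold if the protocol is followed. The documents do not support that.

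- **6.2:** the label is handled by unblinded personnel, and 6.3.2 refers to source documents compiled by the unblinded pharmacist that show individual allocation. The label can go there, and the duty of confidentiality in 6.3.2 covers it.
- **6.3.1:** this section itself says assignment is concealed from investigator staff. Section 6.2 has the unblinded pharmacist or designee obtain the medication numbers, and 6.3.2 describes the IRT as giving allocation to the pharmacist. Section 6.3.3 gives the investigator treatment details only through a code break, which would be pointless if randomization already showed the arm.
- **6.4:** the sentence on the log names nobody. Site personnel appear only in a separate sentence about entering volume, date and time in the eCRF, and none of these is shown to differ by arm. Section 6.2.1 assigns the log to unblinded staff. No fault remains here.

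Nor is it supported that every participant would be unblinded. The return is conditional on material not being destroyed. It covers unused drug, which was given to nobody, and labels carry a medication number but no other participant information. It probably comes after most assessments. The Pharmacy Manual, to which the protocol defers for handling detail, is not among the documents and may say more.

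The consequence is also limited. The primary endpoint is measured by assay, and no inferential analysis is planned (9.2.1).

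All of this narrows the point. None of it removes the return step, because a general duty of confidentiality does not cancel a specific instruction that the investigator returns the log copy.

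**Conclusion.** Section 6.2.1 contradicts 6.3.2 on one step and omits a needed word on another. The step is the return of material by the investigator, where the log copy is the clearest link to individual allocation. The omission is the blind status of the monitors who check accountability. In 6.2 and 6.3.1 the wording is open but compatible with the blind, so those call for clarification only.

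The number of participants affected cannot be estimated: it depends on how many sites return rather than destroy material, when they do so, and whether the investigator reads the log. The exposure is to the descriptive safety and tolerability comparison with placebo. The PK results are little affected.

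The conclusion assumes that the log has participant-level entries and that a return can precede database lock. Both are reasonable readings, but neither is stated outright. A site that destroys its material, files labels with the pharmacist and routes allocation to the pharmacist complies with the protocol and keeps the blind.

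**What to change.** In 6.2.1, make the unblinded pharmacist or unblinded designee responsible for the return, and the unblinded field monitor (or the sponsor address already mentioned) the recipient. In the same section, specify that accountability is monitored by unblinded field monitors, to match 6.3.2.

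Add two clarifications that follow from 6.3.2. In 6.2, say that tear-off labels go into the unblinded pharmacist's restricted source file. In 6.3.1, say that the investigator or delegate receives only a confirmation of randomization from the IRT, and that medication numbers or the saline instruction go only to the unblinded pharmacist. Section 6.4 needs no change.

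The cost is protocol wording, a check that the Pharmacy Manual agrees, and an IRT role setting if one is not already configured. No new staff are needed, since the protocol already provides the unblinded pharmacist and the unblinded monitor.
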